4.1. Study setting/context

Organizations and community-based associations working with socio-economically vulnerable women will be invited to participate. These organizations will be randomly allocated to invite women to either arm 2 or arm 3.

We aim to link the information sessions of the acceptability study to group activities that are offered by the organizations. This was suggested by the community health workers during the focus group discussions as a good way to motivate women to participate. It was reported that it is difficult to gather women for the sole purpose of an information session about their health (especially about cervical cancer that is often not known) and that linking it to an activity for which they are gathered will increase the participation rate.

We are paying attention that organisations and their catchment areas are not too close to each other to avoid spillover.

4.2. Inclusion criteria

4.2.1. Participants

Women who are in a socio-economically vulnerable situation and therefore visit one of the abovementioned organizations. Women from the abovementioned hard-to-reach communities will be invited. They are eligible for inclusion if they meet the following criteria:

- are between the ages of 25 to 65 years of age, in line with the European Guidelines for initiating and stopping cervical cancer screening
- (ever been) sexually active;
- not diagnosed or in treatment for cervical cancer;
- not having had a hysterectomy
- not being pregnant
- Speaking the local language

4.2.2. Community-based researchers offering the interventions

We aim to organize each session including team members with different and complementing backgrounds (medical – social/community – background knowledge specific to the organization). More particularly, we aim that each session is attended by at least 3 team members corresponding with one of each of the following profiles:

- 1) *A researcher with a medical background.* The interventions will be guided by the main researcher in charge of the acceptability study in each study country. The main researcher will take the lead during the educational sessions (arm 2 and 3), give the instructions about self-sampling (arm 3) and will be responsible for the management of the samples (arm 3). The main researcher will be assisted by fellow researchers involved in ELEVATE, including medical students (in the broad sense, including students studying medicine, health promotion, biomedical sciences, etc.). We expect that it will not be feasible for this main researcher to conduct all sessions. Therefore, the main researcher might be replaced by another health care professional (e.g. nurse, physician, medical assistant) or one of the medical students, after they were properly trained and followed some other sessions.

2) *Community-based researchers* will mainly include social workers and community (health) workers. They might not have a medical background but are experienced with working with hard-to-reach women. Community-based researchers will be involved in all stages of this study; however, their core responsibilities will be participant recruitment, assisting during the educational sessions, assisting during self-sampling and (post) counselling, and data collection (questionnaires). They will also be invited to participate in evaluation components of the pilot study (*Obj 6*). Community-based researchers can also help determine which wording will be used for recruitment and data collection.

It is estimated that 3-5 community-based researchers will be required in total.

The general criteria for the selection of community-based researchers include:

- Community and/or social workers experienced in working with socio-economically vulnerable women
- Ages between 21 and 60 (preferably 21-35 years old)
- Speak fluidly the local language
- Extra asset: Speak another language spoken by the target group
- Have communication, research and leadership skills
- Have a good relation with the community
- Have the willingness and the time to collaborate
- Extra asset: female

3) *People that are working or volunteering in the organizations* participating in the acceptability study. These will have a similar profile as the previous group, but additionally they are active in the organization and possibly have a professional relationship with the women. During the focus group discussions, it was reported that trust will be an important facilitator during the information sessions and to encourage women to take a self-sample. Therefore, we aim to invite a familiar face to the information sessions as much as possible. Due to the workload of the organizations, this might not always be possible. However, we will ask if they could express their assent about study participation to women visiting their organization and if possible promote the sessions in their specific working groups or group activities. In addition, we will ask for the organization's support to ensure that all sessions are adapted to the specific target group (culturally sensitive and comprehensible).

4.3. Recruitment of participants

In agreement with the participating organizations, the research team (including the community-based researchers) will hand out invitations (leaflets) to invite women to informative sessions on cervical cancer screening. While handing the invitation, the researcher will shortly describe the goal of the session, emphasizing the benefits for the women. If women are invited for arm 3, they will also be told that they will be offered a self-screening test during the session. Women will receive a leaflet stating the time and place they are expected. Women will be asked to invite other women as well.

We aim to link the sessions to group activities where women are already gathered such as sport activities, integration programs and meals in social restaurants. Therefore, we will work closely with the social

workers and volunteers active in the organizations and will ask for their support to invite women. However, we expect that their contribution will be limited due to their day-to-day workload and tasks.

We will explore with the respective organizations what the best approach is in their context with regard to the timeframe between the invitation and the information session. We learned during the focus group discussions that for many socio-economically vulnerable women it is difficult to commit to show up on another day, for various reasons. Therefore, we aim to organize the educational sessions directly following their group activity, integration class or meal in the restaurant (i.e. the moment they will be invited). In some subgroups of women, such as young mothers, it seems advisable to inform them that they will need to stay a bit longer so they can organize this.

All participants will be offered a small incentive for study participation, such as a voucher.

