3.2. Specific objectives

Objective 1: Assess and compare **attendance rates** following invitation to participate to the study

Hypothesis 1.1: Attendance will be higher when women are offered self-sampling compared to when women are only offered an educational session.

Objective 2: Evaluate the current **knowledge, willingness and uptake** of cervical cancer screening among participants of the acceptability study (arm 2 & 3); assess knowledge improvement and willingness to get screened 3 months after the intervention

Hypothesis 2.1: Knowledge and willingness to get screened will be poor and uptake of cervical cancer screening among the participants will be lower than the national average (but similar to results found in arm 1)

Hypothesis 2.2: After the information sessions, women will be able to link cervical cancer with HPV and will understand the benefit of screening; willingness to be screened will have increased

Objective 3: Assess **attitudes towards and users' experiences** of the HPV self-sampling test among hard-to-reach women (i.e. participants in arm 3)

Hypothesis 3.1: Attitudes towards on-site HPV self-sampling will be overall positive

Hypothesis 3.2: Women who use the self-sampling tool will have positive users' experiences related to the self-sampling device.

Objective 4: Compare the uptake of the on-site HPV testing (arm3) with the current national screening services (arm1) and with off-site referrals (arm2)

Hypothesis 4.1: Uptake of on-site HPV self-sampling will result in an increase in screening coverage compared to standard practices. (arm 3 vs arm 1)

Hypothesis 4.2: On-site HPV self-sampling will have higher uptake than referrals to off-site screening. (arm 3 vs arm 2)

Hypothesis 4.3: Referral to off-site screening following participation in an educational session on cervical cancer will result in higher screening coverage compared to current practices. (arm 2 vs arm 1)

Hypothesis 4.4: Uptake of off-site screening among those who refuse the self-sampling in arm 3 will be lower than uptake of off-site screening in arm 2

Objective 5: Examine the impact of HPV self-sampling on follow-up testing and care

Hypothesis 5.1: Women whose on-site HPV testing came out positive will go for follow-up testing and care

Objective 6: Assess the **feasibility** of the information session and the self-sampling test

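### Peer invitation in section 4.3 does not exclude women from organisations in the other arm, and no described item would reveal it; this weakens the spillover protection of section 4.1

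*Protocol*

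**What the plan says.** The unit of allocation is the organisation. Section 4.1 states: "These organizations will be randomly allocated to invite women to either arm 2 or arm 3". The same section gives the only stated protection between these two arms: "We are paying attention that organisations and their catchment areas are not too close to each other to avoid spillover". It sets no distance or rule.

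Section 4.3 describes leaflets handed out by the research team. On what invitees hear, it says: "If women are invited for arm 3, they will also be told that they will be offered a self-screening test during the session". It then adds the peer step: "Women will be asked to invite other women as well". No limit by organisation, arm or area follows. On timing, it says: "Therefore, we aim to organize the educational sessions directly following their group activity, integration class or meal in the restaurant".

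Section 4.2.1 describes the population as "Women who are in a socio-economically vulnerable situation and therefore visit one of the abovementioned organizations" and goes on to say that women from the hard-to-reach communities will be invited. The listed eligibility criteria mention neither the organisation a woman visits nor earlier attendance at a study session.

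Two hypotheses in section 3.2 compare arm 3 with arm 2. Hypothesis 1.1 reads: "Attendance will be higher when women are offered self-sampling compared to when women are only offered an educational session". Hypothesis 4.2 makes the corresponding claim for uptake, and section 6.1 repeats that comparison as Take-up 2.

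**The concern.** In a comparison allocated by organisation and not blinded, the contrast is protected only as long as women attend under the allocation of their own organisation. Section 4.1 protects this by geography, while the peer step in 4.3 works through personal networks. The two pull against each other.

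The pull is not symmetrical. Only arm 3 advertises a test before attendance, so word passed between women gives a reason to go to an arm 3 session and no comparable reason to go to an arm 2 session. If those who move are readier than average to be screened, arm 3 gains them and arm 2 loses them. Part of the difference tested in Hypotheses 1.1 and 4.2 would then reflect who came rather than what was offered.

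A woman who attends one session of each arm raises a second problem. Under section 6.1, taking the self-test is success in arm 3 and having a Pap smear is success in arm 2. If she self-samples and then sees no need for a Pap smear, she counts as a success in one arm and a failure in the other.

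**Working it through.** The protocol gives no sample size, take-up rate or crossing rate, so there is no figure of its own to reproduce. The check has a textual part and an illustrative part.

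**1. Could a woman from an arm 2 organisation attend an arm 3 session?**
- The instruction in 4.3 does not exclude her.
- The criteria in 4.2.1 do not exclude her: she visits one of the participating organisations, and it need not be the inviting woman's.
- No rule elsewhere says to turn her away.

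So the protocol does not prevent it.

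**2. Would the data show it?**
- The sample code in 4.5.2 holds the centre where the sample was collected, not the organisation the woman normally visits.
- The questionnaire content described in 5.2.2 lists neither home organisation, nor inviter, nor earlier attendance. (The questionnaires themselves are in appendices that are not part of the text at hand.)
- Section 5.2.2.4 keeps names and contacts, but access is confined to the researcher responsible for data collection. Repeat attendance might be found by matching names. A single attendance outside a woman's own organisation would leave no trace.

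**3. What would crossing do to the uptake contrast (Hypothesis 4.2)?** Every rate here is an assumption. Let p2 and p3 be the true uptakes, s the share of arm 2 women who attend arm 3 instead (equal arm sizes), and m2 and m3 the movers' own uptakes under each arm.

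- Observed arm 2 = (p2 − s·m2)/(1 − s)
- Observed arm 3 = (p3 + s·m3)/(1 + s)
- Change in the difference = s(m3 − p3)/(1 + s) + s(m2 − p2)/(1 − s)

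If movers are typical (m2 = p2, m3 = p3), both terms are zero and the difference does not change. If movers are motivated, taken here as m2 = 2·p2 and m3 = 100%:

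| p2, p3 | True difference | s = 5% | s = 10% | s = 20% |
|---|---|---|---|---|
| 20%, 60% | 40 points | 43 | 46 | 52 |
| 30%, 80% | 50 points | 53 | 55 | 61 |
| 50%, 80% | 30 points | 34 | 37 | 46 |

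Worked cell (20%, 60%, s = 20%): arm 2 = (0.20 − 0.08)/0.80 = 0.150; arm 3 = (0.60 + 0.20)/1.20 = 0.667; difference 51.7 points.

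The direction depends on the movers. The first term favours arm 3 whenever movers are readier than average to self-sample. The second favours arm 3 only if they would also have been readier to go for a Pap smear. In the opposite extreme (m2 = 0, m3 = 100%, p2 = 50%, p3 = 80%, s = 10%), the change is 0.1 × 0.2/1.1 − 0.1 × 0.5/0.9 = 1.8 − 5.6 = −3.7 points.

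**4. What would it do to attendance (Hypothesis 1.1)?** Section 5.2.1 divides participants by leaflets handed out. A woman given a leaflet at an arm 2 organisation who goes to arm 3 instead stays in arm 2's denominator and enters arm 3's numerator. More generally, if a share f of attendees are peers without a leaflet, a rate r is computed as r/(1 − f): for r = 40%, f = 10%, 20% and 30% give 44%, 50% and 57%. This applies to peers of any origin and in both arms. It distorts the comparison where peer attendance is heavier in arm 3.

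**The case against.** The strongest reply is that the protocol already makes crossing unlikely. Catchment areas are kept apart. Section 4.4 places sessions in the organisation's own space, its classroom or a nearby room. Section 4.3 aims to hold them straight after the activity at which women are invited, and reports that many of these women find it hard to commit to another day. That leaves little time to bring someone from a distant organisation. This stands, and it limits the risk. It does not remove it: the timing is an aim, 4.3 leaves the interval to be agreed with each organisation, and asking women to invite others serves a purpose only if those others can still come.

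A reader might infer that an eligible peer from outside the inviter's organisation must come from another study organisation. The text does not support that. Section 4.2.1 also speaks of women from the hard-to-reach communities, so a peer may visit no participating organisation, or may visit one in the same arm. Neither woman crosses arms.

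A further reply is that counting each woman once and analysing by allocation are matters for a statistical analysis plan, which is not shown. That is fair as to the analysis rule. But such a rule needs the woman's own organisation and earlier attendance to have been recorded, and whom women are asked to invite is a recruitment rule. Neither can be supplied after recruitment.

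**Conclusion.** The point holds as a gap in a stated recruitment rule. Section 4.3 works against the protocol's own spillover protection, and the data it describes would not show whether crossing had occurred. Bias towards arm 3 in Hypotheses 1.1 and 4.2 is the likelier direction, because only arm 3 advertises a test. For uptake, that direction rests on movers being more motivated than the average woman.

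Two stronger conclusions are tempting and unsupported. One is that 4.3 undoes the protection of 4.1 or offers women a choice of arm: the geographic separation remains, and the protocol offers no choice; it only fails to prevent crossing. The other is that the bias has a known size: the 3 to 16 points added in the table come wholly from assumed uptakes and crossing shares, and fall to zero if movers are typical. Crossing of 20% would be hard to reconcile with separated catchments and same-moment sessions. This is a cheap improvement rather than a defect that invalidates the comparison.

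**What to change.** - **Section 4.3 and the invitation script:** add one sentence telling women not to pass the invitation to women who visit another participating organisation. Peers who visit none may still come, which preserves the reach into unscreened women that peer invitation is meant to give.
- **Eligibility section of the consent form (section 9.4):** add two items: the participating organisation the woman normally visits, if any, and whether she has already attended a study session.
- **Analysis rule:** count each woman once, at her first session, and analyse her by the allocation of her own organisation, or of the inviting organisation if she has none.

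The cost is one sentence, two short items and possibly slightly fewer peer recruits. The protocol gives no basis for putting a number on that last loss.

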5.2.1. Participation registers

Participation registers will be used during the pilot to keep track of the participation rate (*obj 1*).

$$\textit{Participation rate} = \frac{\textit{number of women who participate}}{\textit{number of women who were invited}}$$

The number of women who are invited will be defined by the number of leaflets (invitation letters handed out).

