6.1. Quantitative data

The primary endpoint is the participation in screening which is defined in Arm 1 as the proportion of women who had a PAP smear taken by a GP or gynaecologist within the national screening program, in Arm 2 as the proportion of women who go for PAP smear after attending the information session with targeted referrals for off-site screening and in Arm 3 as the proportion of women who accept to take an HPV self-test on site after the information session.

Two important measures of take-up will be estimated:

Take-up 1 - To compare the take-up of an on-site HPV screening intervention with the current national screening services accounting for self-selection of women who decide to attend clinics (arm 1 vs. arm 3).

Take-up 2 - To compare the take-up of an on-site HPV screening intervention with targeted referrals to off-site screening (population impact regardless of self-selection) (arm 2 vs. arm 3).

Sample calculation was defined according to an estimated increase in take-up compared with current screening coverage for each study country.

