9.1. Protection of subjects

A patient safety plan was developed in order to ensure protection of (potential) participants, including a stigma reduction programme and strategies to tackle harms and emergencies. The stigma reduction programme provides details on ethics and communication training of the researchers involved in the study.

Importantly, the team will ensure that invitations, education sessions and self-sample taking will take place in a confidential environment that provides both visual and auditory privacy. The data collected will only be available to researchers and no third parties will have access to the data.

In addition, the team will ensure that no coercion can be exercised on (potential) participants, by ensuring that participation in the study is voluntary and that refusal to participate in the study will have no repercussion whatsoever. In addition, subjects will be informed that the confidentiality of the data collected in the phone calls and questionnaires is guaranteed.

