9.2. Benefits for the participants

No payment will be offered in exchange for participation in the study, which eliminates the risk of coercion for poor subjects who may feel pressured to participate for financial gain. It will be explained to each participant that their information will help us to improve future cervical cancer screening programs.

The only benefit that participants may receive is information regarding cervical cancer and HPV screening, which will probably lead to increased knowledge and awareness. Such information will be provided during the information sessions and/or if participants have additional questions afterwards.

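### Section 4.3 offers all participants an incentive, while section 9.2 says none is paid and that information is the only benefit, so the no-payment safeguard does not hold as written

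*Protocol*

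**What the plan says.** Section 4.3 (Recruitment of participants) ends with a firm commitment: "All participants will be offered a small incentive for study participation, such as a voucher". It belongs to section 4, which covers arms 2 and 3, so the offer applies to both. The voucher is an example of the form; the incentive itself is not optional.

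Section 9.2 (Benefits for the participants) makes three linked statements:

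- No payment, and what follows from that: "No payment will be offered in exchange for participation in the study, which eliminates the risk of coercion for poor subjects".
- The reason, which concerns women "who may feel pressured to participate for financial gain".
- The full extent of benefit: "The only benefit that participants may receive is information regarding cervical cancer and HPV screening".

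Section 9.1 (Protection of subjects) gives a separate assurance, based on voluntariness and the absence of any repercussion for refusing: "the team will ensure that no coercion can be exercised on (potential) participants".

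Section 4.2.1 defines the population: "Women who are in a socio-economically vulnerable situation and therefore visit one of the abovementioned organizations".

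**The concern.** The women invited are chosen because they are socio-economically vulnerable. Section 9.2 names poor women as the group it protects, and the protection it cites is that they have nothing financial to gain. Section 4.3 gives them something of value for taking part. The ethics argument in 9.2 then rests on a condition that the recruitment plan does not meet.

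There is also an operational problem. The study runs in four countries. A site that follows 4.3 hands out an incentive; a site that follows 9.2 does not. An incentive for taking part bears on whether women come, and attendance is the outcome of Objective 1. If sites differ, their attendance rates are not measured under the same conditions. If all sites give it, the rates describe an incentivised invitation, and 9.2 tells the reader otherwise.

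**Working it through.** The protocol gives no value for the incentive and no expected attendance or uptake with and without it. There is no figure to reproduce, so the check is a comparison of the text.

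**1. Do 4.3 and 9.2 conflict?**

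| Question | Section 4.3 | Section 9.2 |
|---|---|---|
| Is anything of value offered for taking part? | Yes, to all participants | No payment |
| What do participants gain? | A small incentive, for example a voucher | Information only |
| Could a poor woman take part for financial gain? | Possible | Said to be eliminated |

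The rows disagree. No section separates a voucher from a payment or limits the incentive to expenses. The protocol is one document dated June 2022 with no amendment log, so neither statement is superseded.

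**2. Does a narrow meaning of payment remove the conflict?** Suppose payment means cash. The first row can then be reconciled, but the second cannot: a voucher is a benefit other than information. The third also remains, because the reasoning in 9.2 depends on there being no financial gain, and a voucher is a gain of that kind.

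**3. Which safeguard is affected?** Only the no-payment one. The assurance in 9.1 does not depend on the absence of an incentive.

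**4. Which outcome is exposed?** Section 5.2.1 says: "Participation registers will be used during the pilot to keep track of the participation rate". That rate is women who participate divided by women invited, counted by leaflets handed out. An incentive tied to participation acts on the numerator, so attendance is directly exposed.

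The primary endpoint in section 6.1 is defined after the session. For arm 3 it reads: "in Arm 3 as the proportion of women who accept to take an HPV self-test on site after the information session". Section 3.1 likewise sets self-sampling uptake against the women who attend. More attenders do not by themselves change this proportion. An illustration with assumed figures, not from the protocol: of 100 women invited, attendance rises from 50 to 60 and 80% of attenders self-sample.

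- Without incentive: attendance 50/100 = 50%; uptake 40/50 = 80%.
- With incentive: attendance 60/100 = 60%; uptake 48/60 = 80%.

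Attendance moves by 10 points and uptake by none. If the added attenders were less willing to self-sample than the others, uptake would fall; if more willing, it would rise. The protocol does not allow the direction to be determined.

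**5. Which comparisons differ in exposure?** Arm 1 consists of coverage rates collected before the study starts, with no study incentive. Hypotheses 4.1 (arm 3 vs arm 1) and 4.3 (arm 2 vs arm 1) therefore set women recruited with an incentive against a population without one. In arm 3 vs arm 2 the offer is made in both arms, so that contrast is less exposed, provided the incentive is the same in each.

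**The case against.** The strongest reply is that this is a wording slip with no demonstrated effect on the primary results. Much of that stands:

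- The protocol does not say that the self-sample is incentivised. A reader might infer it, because section 4.3 does not say when the incentive is given. But the offer is to all participants, and sections 4.6 and 5.2.2 count arm 3 women who do not self-sample as participants. The natural reading is an incentive that does not depend on the sample. The unstated timing is a gap, not evidence of the contrary.
- A reader might also infer that the contrasts with arm 1 are inflated by whatever the incentive adds to attendance. The endpoint definitions do not support this, as the illustration shows.
- The effect on hypothesis 4.3 is speculative. Arm 2 uptake is an off-site Pap smear checked by phone at 3 months, and nothing links the incentive to that appointment.
- It cannot be said that participants are misinformed. The information sheet is not shown. Section 9.4 lists its topics, which include benefits and risks, but not what it says about an incentive. An ethics committee reading the whole protocol would see both sections.
- The voluntariness safeguard in 9.1 is intact.

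What the reply does not remove is the contradiction itself. The two sections cannot both be followed, and 9.2 makes an absolute claim on a premise that 4.3 denies.

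**Conclusion.** The contradiction is certain and affects every participant in arms 2 and 3. As written, the protocol claims a no-payment protection for poor women that its own recruitment section removes. This conclusion rests only on the text of 4.3 and 9.2 and holds even if payment is read as cash.

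The consequence for results is limited to what the text supports. If 4.3 is followed, attendance under Objective 1 is measured with an incentive. The comparisons with arm 1 are between women recruited with an incentive and a population without one, which the protocol does not acknowledge. Neither the size nor, for uptake, the direction of any effect can be derived from the document. The point should be corrected, but it does not show that the primary comparison is biased.

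**What to change.** Reconcile sections 4.3 and 9.2 in one of two ways:

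1. Remove the incentive from 4.3 and leave 9.2 as it is.
2. Keep the incentive. Delete from 9.2 the statements that no payment is made, that the risk of coercion is thereby eliminated and that information is the sole benefit, and describe the incentive there instead.

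In either case, check that the information sheet agrees with the text that is kept.

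Under the second option, also state that the incentive is the same in arms 2 and 3 and is given for attending the session, regardless of the decision to self-sample. This puts the natural reading of 4.3 in writing and keeps the arm 3 vs arm 2 contrast clean. Add one line of interpretation: attendance, and the comparisons with arm 1, are to be read knowing that arms 2 and 3 were incentivised and arm 1 was not.

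The cost is a few sentences in 4.3 and 9.2, a check of the information sheet and one line on interpretation. No extra data, participants or analyses are needed.
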